### Safety analysis

The safety and tolerability profile will be assessed versus baseline conditions and differences between treatment groups and descriptive statistics will be produced for both values and change from baseline, where applicable.

Extent of exposure and compliance will be evaluated.

Concomitant medications will be summarized using the World Health Organization (WHO) Drug Dictionary with frequencies and percentages for each treatment group. All medications administered between the date of the first dose and the end of the study will be included.

An analysis of the TEAEs will be done. AEs will be summarized using the Medical Dictionary for Regulatory Activities (MedDRA) tabulated by preferred term and system organ class. TEAEs will be summarized with frequencies and percentages for each treatment group. Tabulations by severity and drug-relatedness will also be made.

Laboratory parameters values will be summarized for each visit for each treatment group including within-group changes from baseline.

BMD values and corresponding Z-scores will be summarized at baseline and at Month 6 for each treatment group, using the observed data. The within-group percent changes from baseline for BMD values will also be summarized, including 2-sided 95% confidence intervals. Categorical summaries of percent change from baseline will also be produced. The percent changes from baseline to Month 6 will be compared between each of the linzagolix groups and the placebo group via analysis of co-

variance with treatment group as the main effect (three values) and including the baseline as a covariate.

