### 13.5.5 Safety Analysis

The safety and tolerability profile will be assessed versus baseline conditions and differences between treatment groups and descriptive statistics will be produced for both values and change from baseline, where applicable.

Extent of exposure and compliance to treatment will be evaluated.

Concomitant medications will be summarized using the World Health Organization (WHO) Drug Dictionary with frequencies and percentages for each treatment group. All medications administered between the date of the first dose of study drug and the date of the last dose of study drug, inclusive, (i.e., all medications starting or ongoing during the time interval) will be included. Thus, all medications with an end date prior to the first study drug dose will be excluded from the summary table.

An analysis of the TEAEs will be done. AEs will be summarized using the Medical Dictionary for Regulatory Activities tabulated by (MedDRA) dictionary preferred term and system organ class. TEAEs will be summarized with frequencies and percentages for each treatment group. TEAEs are defined as AEs with a start date on or after the first dose of study drug. Adverse events starting more than 30 days following discontinuation of study drug will not be included in summaries of TEAEs but will be summarized separately as post-treatment AEs. Tabulations by severity and drug-relatedness will also be made.

Laboratory parameters values will be summarized for each visit for each treatment group including within-group changes from baseline. Evaluation of shifts for changes from baseline according to the normal range will be provided.

BMD values and corresponding Z-scores will be summarized at baseline and at Month 6 for each treatment group, using the observed data. The within-group percent changes from baseline for BMD values will also be summarized, including 2-sided 95% confidence intervals. Categorical summaries of percent change from baseline will also be produced. The percent changes from baseline to Month 6 will be compared between each of the linzagolix groups and the placebo group via analysis of co-variance with treatment group as the main effect (three values) and including the baseline as a covariate. Sub-group analyses based on demographic and baseline characteristics will be performed for BMD, and will be specified in the SAP. The Safety Analysis Set shall be used when summarizing safety data.

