1.2. Objectives of Statistical Analysis

Following the early termination of the study and due to the number of subjects randomized being substantially lower than the target number if the study had been fully enrolled, this statistical analysis plan (SAP) is focused on the safety analysis and all safety and efficacy data will be presented in listings. Consequently, this SAP is designed to outline the methods to be used in the analysis of study data to answer the safety and tolerability objectives.

The primary objective of this study was to demonstrate the efficacy and safety of linzagolix administered orally once daily for up to 3 months at a dose of 75 mg alone or of 200 mg in combination with ABT (E2 1 mg / NETA 0.5 mg) versus placebo, while under randomized treatment, in the management of moderate to severe EAP in women with surgically confirmed endometriosis. The two co-primary efficacy endpoints were clinically meaningful reduction over the last 28 days of randomized treatment up to the Month 3 visit along with a stable or decreased use of analgesics for EAP for 1) DYS and for 2) NMPP.

Secondary objectives included evaluation of persistence of efficacy over the last 28 days of randomized treatment up to the Month 6 visit, evaluation of pain associated with sexual intercourse (dyspareunia) and defecation (dyschezia), difficulty of doing daily activities, analgesic use, assessment of subject perception of severity, change in uterine bleeding, Quality of Life (QoL) questionnaires, pharmacoeconomic burden of endometriosis by assessing changes in patient productivity, assessment of endometriosis related number of non-study health visits, number of days in hospital and type of medical procedures performed during the Treatment Period.

Safety and tolerability objectives included assessment of BMD, endometrial health, cardiac safety including QT interval prolongation, standard laboratory safety parameters, gynecological assessments and AE frequency including specific hypoestrogenic AEs.

Exploratory objectives included assessment of bone turnover markers and collection of PK and PD data of linzagolix for a separate modelling exercise.

Populations for analysis, data handling rules, statistical methods, and formats for data presentation are provided. The statistical analyses and summary tabulations described in this SAP will provide the basis for the results sections of the clinical study report (CSR) for this trial.

Statistical Analysis Plan

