The efficacy variables planned in the protocol will not be analyzed due to the early study termination and the low number of subjects randomized.

2.5.2. **Pharmacokinetic Variables**

The pharmacokinetic variables planned in the protocol will not be analyzed due to the early study termination and the low number of subjects randomized.

2.5.3. **Safety Variables**

Safety endpoints include:

- Change from baseline to each scheduled assessment in BMD measured by DXA of lumbar spine (L1-L4), femoral neck, and total hip
- Incidence and severity of treatment emergent adverse events (TEAEs)
- Incidence and severity of hypoestrogenic TEAEs (hot flush)
- Time to the first post-treatment menses
- Changes in clinical laboratory assessments (hematology, biochemistry, coagulation parameters, hormones, lipids and urinalysis) from baseline to each scheduled assessment
- Any pathological changes from baseline in the endometrium as assessed by histology from endometrial biopsies
- Changes from baseline to each scheduled assessment in any other safety parameter including weight, vital signs, ECG, gynecological assessments and endometrial thickness

Safety analyses are described in Section 4.8.

Note that the endpoint “Time to the first post-treatment menses” was initially planned in the protocol, but will not be described in this SAP, because the study was stopped prematurely, and all subjects couldn’t be followed to evaluate this endpoint.

2.5.4. **Exploratory Variables**

The exploratory variables planned in the protocol will not be analyzed due to the early study termination and the low number of subjects randomized.

Sponsor:	ObsEva		
Protocol:	18-OBE2109-002		
Document Version No.:	1.0	Document Date:	18-MAY-2021

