4.2.4. Adjustments for Covariates

Not Applicable

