The number of events will be also displayed for summary of AEs, for analysis of TEAE, serious TEAE non-serious TEAE and for post-treatment AE, by SOC and PT.

No formal hypothesis-testing analysis of adverse events incidence rates will be performed.

All adverse events occurring on study will be listed in subject data listings.

By-subject listings also will be provided for the following: Treatment Emergent Adverse event, serious Treatment Emergent adverse events; Treatment Emergent adverse events leading to permanent discontinuation of IMP and leading to permanent discontinuation of IMP leading to death; post-treatment adverse event.

Sponsor:	ObsEva		
Protocol:	18-OBE2109-002		
Document Version No.:	1.0	Document Date:	18-MAY-2021

4.8.3. **Bone Mineral Density (BMD) by DXA**

BMD of femoral neck, total hip and lumbar spine will be assessed by DXA at Baseline, Month 6 and Month 6 follow-up. Unacceptable DXA assessments (accepted="No") will not be summarized (hip, spine and femur considered separately).

In case of repeated values due to BMD loss $\geq 5\%$, the initial scan will be used in summaries. Initial and repeated scan values will be reported in the listings.

Calibrated values will be used if available, otherwise initial values will be considered.

BMD, expressed as both absolute values and Z-scores will be summarized at each visit in terms of actual values, changes from baseline for each anatomic location. For absolute values only, percent change from baseline and 95% confidence interval for the mean percent change from baseline within each group will be produced at each time point.

Percent change from baseline to Month 6 and Month 6 follow-up will be described and will also be summarized in categories of percentage with the following classes:

- No change or increase,
- Decrease $\leq 3\%$,
- Decrease $> 3\% \text{ and } \leq 5\%$,
- Decrease $> 5\% \text{ and } \leq 7\%$,
- Decrease $> 7\% \text{ and } \leq 8\%$,
- Decrease $> 8\%$.

All data will be listed.

4.8.4. **Laboratory Data**

Clinical laboratory values will be expressed using conventional SI units.

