5. CHANGES TO PLANNED ANALYSES

Following the early termination of the study and due to the number of subjects randomized being really less than the target number if the study had been fully enrolled, the analyses planned in the protocol on efficacy and pharmacokinetic assessments have been removed and only listings for these assessments will be displayed. The statistical analysis plan (SAP) will be focused on the safety analysis and all safety.

For safety endpoints, the endpoint “Time to the first post-treatment menses” was initially planned in the protocol, but will not be described in this SAP, because the study was stopped prematurely and all subjects couldn’t be followed to evaluate this endpoint.

Sponsor:	ObsEva		
Protocol:	18-OBE2109-002		
Document Version No.:	1.0	Document Date:	18-MAY-2021

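### SAP 4.8.3 drops the protocol's linzagolix-versus-placebo BMD comparison, and Section 5 declares neither that removal nor the loss of the BMD subgroups

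*SAP*

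**What the plan says.** Protocol 13.5.5 first asks for BMD summaries, within-group percent changes with 95% confidence intervals, and categories of change. It then adds a between-group analysis: percent change to Month 6 "will be compared between each of the linzagolix groups and the placebo group via analysis of co-variance", with a three-level treatment factor and baseline as covariate. The synopsis says the same: "The percent changes from baseline to Month 6 will be compared between each of the linzagolix groups and the placebo group". Protocol 13.5.5 also states: "Sub-group analyses based on demographic and baseline characteristics will be performed for BMD", leaving the details to the SAP.

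SAP 1.2 explains that the trial stopped early with far fewer women randomised than planned, so "this statistical analysis plan (SAP) is focused on the safety analysis and all safety and efficacy data will be presented in listings". BMD remains a listed safety endpoint in SAP 2.5.3: "Change from baseline to each scheduled assessment in BMD measured by DXA of lumbar spine (L1-L4), femoral neck, and total hip".

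For the BMD analysis, SAP 4.8.3 provides actual values, changes, percent changes, categories of percent change, and a "95% confidence interval for the mean percent change from baseline within each group will be produced". SAP Section 5 states that "the analyses planned in the protocol on efficacy and pharmacokinetic assessments have been removed". The only safety item it names as dropped is time to first post-treatment menses.

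**The concern.** BMD is a central safety question in this programme. Protocol 5.3 and 5.5.3 give BMD loss on 200 mg alone as the reason for pairing that dose with add-back therapy. A report focused on safety is where a reader would look for the effect of each regimen on bone relative to placebo.

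Within-arm change does not isolate that effect. Every arm is supplied with calcium and vitamin D to limit bone loss (Protocol 10.6.1), so any change common to all arms is mixed into each arm's mean. The placebo arm is there to separate the two, and the protocol planned to use it that way.

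There is also a transparency problem. Section 5 names one dropped safety endpoint, so a reader would reasonably take the other planned safety analyses as intact.

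**Working it through.** **1. Is the comparison still planned anywhere?** The plans set side by side:

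| Protocol 13.5.5, BMD | SAP 4.8.3 and table list in 7.2 |
|---|---|
| Values and Z-scores by group | Kept (Tables 14.4.1.1.1 and 14.4.1.3.1) |
| Within-group percent change with 95% CI | Kept |
| Categories of percent change | Kept (Table 14.4.1.2.1) |
| ANCOVA, each linzagolix arm versus placebo, Month 6 | Absent from text and tables |
| Subgroup analyses | Absent from text and tables |

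**2. Is the removal declared or explained anywhere?**

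- SAP 1.2 gives low enrolment as the general reason for a reduced plan and says differences from the protocol will be outlined. It does not apply the reason to BMD.
- SAP 4.2.4 (covariates) and 4.2.6 (subpopulations) are marked as not applicable, with no reason and no mention of BMD.
- SAP 4.2.5 drops multiplicity because only safety will be analysed. That does not explain removing a safety analysis.
- The statements that nothing will be formally compared are confined to baseline data (4.5) and adverse event rates (4.8.2).
- Section 5 covers efficacy, pharmacokinetics and time to menses. BMD is none of these.

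**3. How precise would the restored contrast be?** The plan gives no figure to reproduce. Its stated design power concerns the pain endpoints and has no bearing on BMD. The number randomised is not given. Protocol 5.5.3 gives a Phase 2b interval for 75 mg (-1.57 to -0.03), which implies a standard error of 1.54 / (2 × 1.96) = 0.39, but without the group size no SD follows. Both n and SD are therefore assumptions.

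For a three-arm ANCOVA with one covariate and n women per arm, assuming the covariate gains no precision:

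half-width = t(q, 3n − 4) × SD × √(2/n), with q = 0.975 for a 95% interval.

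At n = 10 and SD = 3: t(0.975, 26) = 2.056, √(2/10) = 0.447, so 2.056 × 3 × 0.447 = 2.76 percentage points.

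| Level, SD (points) | n = 10 | n = 15 | n = 25 | n = 40 |
|---|---|---|---|---|
| 95%, SD 2.5 | 2.30 | 1.84 | 1.41 | 1.11 |
| 95%, SD 3.0 | 2.76 | 2.21 | 1.69 | 1.33 |
| 95%, SD 3.5 | 3.22 | 2.58 | 1.97 | 1.55 |
| 97.5%, SD 3.0 | 3.19 | 2.55 | 1.94 | 1.52 |

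**4. Which women would the estimate rest on?** SAP 4.2.10 takes as the Month 6 scan the first accepted one from Day 169 − 28 = 141 to Day 169 + 28 = 197. Protocol 10.7.2 requires no DXA of women who stop before Month 3. Women who stop later have one at withdrawal, but a scan on Days 85–140 falls before the window. That is 56 of the 84 days from Day 85 to Day 168 (56/84 = 0.67). This is a count of calendar days, not of women, and it treats the scan as done on the day of stopping. SAP 3.1 analyses the Safety Set by treatment received.

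**The case against.** The best case for the SAP is that it became descriptive throughout, for a reason stated up front. Marking covariates and subpopulations as not applicable signals the removal, if tersely. Database lock and unblinding are written as still to come, so nothing suggests the choice followed the results. The placebo arm is not lost either: each arm gets its n, mean and SD (SAP 4.2.1) and its own interval, and by-subject values are listed. A reader can work out a crude difference.

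Precision is the strongest part of the objection. The Phase 2b spine change quoted for 75 mg is −0.8%. The smallest 95% half-width above is 1.11, so on these assumptions a difference of that size could not be told from zero. The scan window and the treatment-received basis also limit the within-arm summaries that the SAP keeps, so they are not specific to the contrast.

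Much of this is right. It rules out any claim of significance, and it means the interval may tell the reader little. It does not justify leaving the difference out, because SAP 4.8.3 already prints intervals on the same women at the same small n. Nor would the contrast always be empty. Protocol 5.6 reports −2.602% at the lumbar spine on 200 mg alone. With SD 3 and an estimated difference of zero, 40 per arm would exclude a loss that large (half-width 1.33) and 10 per arm would not (2.76). And the general reason in SAP 1.2 does not tell the reader that a planned BMD comparison and the BMD subgroups are gone.

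**Conclusion.** The concern holds. A prespecified, placebo-controlled safety analysis of BMD, and the BMD subgroups with it, were removed without being declared. The report would print no difference from placebo and no interval for one.

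That the analyses are missing and undeclared follows from the text alone. The size of the loss cannot be fixed from the documents. Over assumed SDs of 2.5 to 3.5 points and 10 to 40 women per arm, the 95% half-width runs from 1.1 to 3.2 points, so the estimate could be useful or nearly uninformative. Even when restored, it would not be a full randomised comparison, given the scan window and the treatment-received basis. This is a change that should be made, though it does not undermine the rest of the SAP.

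**What to change.** - **SAP 4.8.3:** restore the protocol's ANCOVA (treatment group, baseline BMD) of percent change to Month 6 at lumbar spine, femoral neck and total hip. Report each adjusted difference from placebo with a two-sided interval and make no significance claim. State the level. 95% is the natural descriptive choice, since it matches the BMD intervals already in Protocol 13.5.5 and SAP 4.8.3; 97.5% would match Protocol 13.1.
- **Beside the estimate:** say that it rests on women with an accepted scan on Days 141–197, by treatment received, and leaves out women who stopped before Month 3 and withdrawal scans before Day 141.
- **SAP 4.2.4 and 7.2:** amend the covariate entry and add the table.
- **SAP Section 5:** state that the BMD subgroups are dropped because of low enrolment. If the sponsor decides against the ANCOVA, name that removal and its reason there too.

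The cost is SAP wording, one table and one model per site, on data already collected. The downside is intervals that may be too wide to say much.

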#### **10.2.2.5 Study visit: Month 6 (day 169 ± 3 days)**

The following tests and evaluations will be performed :

- eDiary completion compliance check
- ePRO and ClinRO completion, ideally before any other procedures or assessments: EHP-30, HRPQ, HRUQ, PSIQ, SSIQ, PROMIS, EQ-5D-5L, specific monthly severity questions, mPGIS, PGIC completion (anchors must be completed last)
- Concomitant treatments recording
- AE recording
- Completion of the paper C-SSRS questionnaire (version for “already enrolled subjects” (see Appendix S) for patients responding to the C-SSRS for the first time during the study, or version “since last study visit” (see Appendix T) for patients for whom the C-SSRS was completed at the previous study visit)
- Final IMP accountability based on blisters
- ECG (at about the same time as but before the PK sample)
- Physical examination, including weight recording
- Vital signs (BP and heart rate)
- Urine pregnancy test
- Gynecological examination
- Manual breast examination (by palpation)

- TVUS of uterus
- Urinary protein dipstick
- Fasting (overnight) blood samples for haematology, coagulation parameters, chemistry, lipids, hormones and bone biomarkers
- Pre-dose PK samples (the time of dose administration on previous 4 days and time of PK sampling will be recorded)
- Endometrial biopsy, unless the endometrium thickness in TVUS is  $\leq 5$  mm, in which case no endometrial biopsy will be necessary (see section 10.4.5). Appropriate photo documentation of the endometrium thickness is mandatory.
- BMD assessed by DXA for femoral neck, hip and spine. DXA can be performed up to 10 days prior to the study visit which allows to get the DXA results ideally at the time of the Month 6 study visit at the latest, knowing that subjects who experience more than 8% BMD loss or a Z-score  $\leq -2.5$  will not be eligible to enter the extension study.
- The subject will be verbally asked which treatment she believed she received during the blinded Treatment Period. The answer will be recorded in the eCRF.
- Contraception dispensing (if applicable) and counselling

An additional question will be asked to the subject about the burden of filling in the eDiary (0 = not at all a burden, 10 = very much a burden). The answer will be recorded in the eCRF.

Study visit Month 6 constitutes the end of the Treatment Period.

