## 11.2 DOSAGE AND ADMINISTRATION

Linzagolix and corresponding placebo treatments will be supplied as film-coated tablets for oral administration and given as monthly treatment kits (Figure 5).

ABT and corresponding placebo will be supplied as red capsules and given as 3-monthly treatment kits.

IMP treatment will start on Day 1 and will be administered once daily up to the day preceding the Month 6 visit. The subjects will have to swallow two tablets of linzagolix/placebo and one capsule of ABT/placebo, ideally at the same time each day.

On the day of a study visit, the subject must take the study medication at site, after the PK blood sample collection, except on Day 1 visit where the study medication must be taken before the PK blood sample collection (at least 1.5 h before). The site staff will record in the eCRF the time of study medication intake. The linzagolix/placebo tablets must be taken from the kits dispensed on that visit (and not from the previously dispensed kits). On Day 1 and Month 3 visits, ABT/placebo capsules must be taken from the kits dispensed during these visits. On Month 1, 2, 4 and 5 visits, ABT/placebo capsules must be taken from the previously dispensed kits.

The treatment groups are described below:

Treatment group	Daily dose Day 1 to Month 6			
	Linzagolix active tablets	Linzagolix placebo tablets	ABT active capsules	ABT placebo capsules
75 mg	1 × 75 mg	1 × placebo 200 mg	None	1 capsule
200 mg	1 × 200 mg	1 × placebo 75 mg	1 capsule	None
Placebo	None	1 × placebo 75 mg AND 1 × placebo 200 mg	None	1 capsule

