4.2.12. Last treatment administration date, End of Study date and Period definitions

The last treatment administration date will be defined as the date of treatment termination recorded in the main period eCRF page. If this date is missing, the last date with a drug intake in eDiary prior to the Month 6 date or, for subjects who discontinued, the last date with available drug intake information in the subject eDiary will be used.

The end of study date will be the last assessment date in the main study defined as last eCRF or ediary date prior to and not including Month 6 for subjects who entered the Extension, and the last eCRF or ediary date in the main study or main follow-up if not. This will not necessarily be the same date as last assessment date as recorded in the eCRF.

Note: For summaries by visit (efficacy or safety), the Month 6 assessments will be included in the main study analyses. For Adverse Events, Concomitant Medications and Daily diaries, data collected on Month 6 date will be part of the extension for subjects entering the extension study and be part of the Follow-up period for subjects entering the main study follow-up period.

The main treatment period will be defined as Day 1 up to (Month 6 date -1) or the treatment discontinuation date.

The main follow-up period will be defined as the Month 6 date or (treatment discontinuation date+1) up to the end of study date (for subjects who entered into the main follow-up period).

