Hematology, coagulation parameters, chemistry and lipids were assessed at screening and at each visit during the treatment period, as well as at the M1 FU and M3 FU visits. E2, progesterone (P4) and LH are assessed at each visit during the treatment period (not at screening visit), as well as at the M1 FU and M3 FU visits. Serum levels of the anti-Müllerian hormone (AMH) and fasting glucose were assessed on Day 1 only. Serum levels of the sex hormone-binding globulin (SHBG) were assessed on Day 1 and Month 3 and Month 6 visits.

Blood samples were to be analyzed by the central laboratory.

For hematology, coagulation parameters, chemistry and lipids, the actual value and change from baseline will be summarized for each visit for each treatment group. In the event of repeated values, the last non-missing value per study day/time will be used.

Evaluation of shifts for changes from baseline to all visits, and to last on-treatment value (including unscheduled assessments) according to the normal ranges with categories "Low", "Normal", "High"

Sponsor:	ObsEva		
Protocol:	18-OBE2109-002		
Document Version No.:	1.0	Document Date:	18-MAY-2021

and according to normal/abnormal/abnormal clinically significant information collected otherwise, will be provided. Note that a value will be considered as “on-treatment” if the collection is performed between the first and last intake administration (included).

For Liver Function Test (LFT) parameters (ALT, AST, ALP, total bilirubin, direct bilirubin, indirect bilirubin, GGT, albumin, LDH and Creatine Kinase), evaluation of shifts for changes from baseline will be extended by the worst (highest) on-treatment value (including unscheduled assessments) according to the normal ranges with categories “Low”, “Normal”, “High” will be provided.

For the lipid panel (Triglycerides, HDL, LDL, Total Cholesterol, LDL/HDL ratio), the percent change from baseline to each on-study visit will also be summarized.

For serum levels of P4, SHBG and LH, only the actual values at each time point will be summarized. Note: in the event of repeated values, the last non-missing value per study day/time will be used.

In addition, for E2, the proportion of subjects with the following categories:

- E2 <20 pg/mL,
- E2 between ≥20 and <60 pg/mL,
- E2 ≥60 pg/mL

at each visit and for each treatment group will be provided in tables.

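### SAP 4.8.4 closes the on-treatment window at the last dose, so a completer's Month 6 labs can miss the last-value and worst-value shift rows by one day; for albumin, highest is also the wrong worst value

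*SAP*

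**What the plan says.** The on-treatment rule is in SAP 4.8.4 (Laboratory Data): a value qualifies "if the collection is performed between the first and last intake administration (included". Two shift summaries use it. One is the shift from baseline to the last on-treatment value, for hematology, coagulation, chemistry and lipids. The other is for the liver panel, whose parameter list ends "GGT, albumin, LDH and Creatine Kinase), evaluation of shifts for changes from baseline will be extended by the worst (highest) on-treatment value". Albumin is in that list with no direction of its own.

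On the end of dosing, Protocol 11.2 says "IMP treatment will start on Day 1 and will be administered once daily up to the day preceding the Month 6 visit". SAP 4.2.12 matches this: "The main treatment period will be defined as Day 1 up to (Month 6 date -1) or the treatment discontinuation date". The last-dose date itself comes first from the eCRF: "The last treatment administration date will be defined as the date of treatment termination recorded in the main period eCRF page". If that is missing, the fallback for completers is "the last date with a drug intake in eDiary prior to the Month 6 date".

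The Month 6 laboratory samples are taken at the visit. Protocol 10.2.2.5 lists "Fasting (overnight) blood samples for haematology, coagulation parameters, chemistry, lipids, hormones and bone biomarkers". For by-visit output, SAP 4.2.12 keeps them: "For summaries by visit (efficacy or safety), the Month 6 assessments will be included in the main study analyses".

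**The concern.** The Month 6 sample is the end-of-treatment sample, yet two of the rows meant to describe laboratory changes on treatment can exclude it by one day. Its timing relative to dosing is not unusual. At Months 1 to 5 the dose is taken at the site after the pre-dose PK sample, so safety blood drawn with that sample is also about a day after the previous dose, and it counts.

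Classification also depends on a date field. If a site enters the day before Month 6 as treatment termination, the sample is out; if it enters the Month 6 date, the same sample is in. Two completers with identical visits can therefore be classified differently.

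Samples at a withdrawal visit held a day or more after the last dose are excluded too. Protocol 10.7.2 foresees such gaps, since it waives PK sampling when no dose was taken the day before. Any of these samples that the ±14-day rule in SAP 4.2.10 does not map to a visit appear only in listings.

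The SAP is now focused on safety, and the worst-value row is the only laboratory shift row that takes the worst result across visits. By-visit shifts do not show whether a subject who is High at Month 6 was already High earlier. Where high is the adverse direction, leaving out a sample can only lower the worst category. For albumin, a rule that takes the highest value shows Low only if every on-treatment value is low.

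**Working it through.** **Visit days (Protocol 10.2).** Visit day = 1 + 28 × month. Month 6 = 1 + 168 = Day 169 and Month 5 = 1 + 140 = Day 141, as the protocol states. The visit window is ±3 days.

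**The one-day miss.** Planned last dose = Month 6 visit day − 1.

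| Month 6 visit | Last dose | Gap to sample | Scheduled samples on-treatment | If the eCRF termination date is the Month 6 date |
|---|---|---|---|---|
| Day 166 | Day 165 | 1 day | Months 1–5 | Months 1–6 |
| Day 169 | Day 168 | 1 day | Months 1–5 | Months 1–6 |
| Day 172 | Day 171 | 1 day | Months 1–5 | Months 1–6 |

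The gap is one day whatever the visit date, because the last dose is tied to the visit. The eDiary fallback for completers always gives a date before Month 6, so under it the sample is always excluded.

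**Last-value row.** The last scheduled on-treatment sample becomes Month 5, 168 − 141 = 27 days before the last dose. With the windows this is 165 − 144 = 21 to 171 − 138 = 33 days. I claim no percentage for this row: at a constant abnormality rate, changes run in both directions and the expected net shift is zero.

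**Worst-value row, parameters where high is adverse.** The category is lowered when Months 1–5 are normal and Month 6 is abnormal. The documents give no abnormality rates, so the per-visit rate p is assumed. Unscheduled samples, which the row also takes, are ignored.

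- Independent visits: p(1 − p)^5.
- Stationary two-state chain with visit-to-visit correlation r: (1 − p) × (1 − p(1 − r))^4 × p(1 − r).

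| p per visit | Independent | r = 0.5 | r = 1 |
|---|---|---|---|
| 2% | 0.02 × 0.98^5 = 1.8% | 0.98 × 0.99^4 × 0.01 = 0.9% | 0% |
| 5% | 0.05 × 0.95^5 = 3.9% | 0.95 × 0.975^4 × 0.025 = 2.1% | 0% |
| 10% | 0.10 × 0.90^5 = 5.9% | 0.90 × 0.95^4 × 0.05 = 3.7% | 0% |

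If the rate is 5% at Months 1–5 and 10% at Month 6, independent visits give 0.10 × 0.95^5 = 7.7%.

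These are percentages of affected completers, per parameter. If half of completers have the Month 6 date entered as termination (assumed), the 5% figures over all completers become 0.5 × 3.87% = 1.9% (independent) and 0.5 × 2.15% = 1.1% (r = 0.5). If all do, they are 0%.

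**Albumin.** For the series Normal, Low, Low, Low, Normal, the highest category is Normal and the lowest is Low. A subject Low at 4 of 5 on-treatment samples, or at 5 of 6 with Month 6 included, is shown as not Low.

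**Length of a tail.** Protocol 5.5.1 gives a linzagolix half-life of about 15–20 hours. Five half-lives are 75–100 hours, or 3.1–4.2 days, which is within 7 days.

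**The case against.** The strongest reply is that the premise rests on a field the documents do not show. The last-dose date comes first from the eCRF, and its completion instructions are not available. Parts of the protocol also point to a dose at Month 6: 10.2.2.1 and 11.2 have the dose taken at site on visit days, and 10.2.2.5 calls the Month 6 PK sample pre-dose. If sites record the Month 6 date, completers lose nothing. This stands as a condition on the finding, and it also shows why inconsistent entry is foreseeable.

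Second, little is hidden. Month 6 stays in the by-visit shifts and the listings. Clinically significant abnormalities are reported as adverse events (Protocol 10.4.8) and can reach the TEAE tables. Low albumin remains visible in the by-visit and last-value rows. The rule is the same in every arm and the tables are descriptive. All of this is right and limits the severity, but by-visit rows do not replace a worst-across-visits row.

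Third, few subjects are involved. Enrolment stopped well short of target and the number of completers is not given. With an assumed 10 to 40 affected completers per arm, 3.87% is 0.39 to 1.55 subjects per parameter and 2.15% is 0.22 to 0.86. That is fair.

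Fourth, a 7-day tail is more than the one-day miss needs, and its half-life support covers linzagolix only, although one arm also takes E2/NETA. That is also fair: a one-day extension would restore 6 of 6 scheduled samples. The longer tail is there for withdrawal samples.

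Finally, the documents do not state albumin's adverse direction. That low is the direction of interest in a liver panel is general clinical knowledge; the masking of low values follows from the text alone.

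**Conclusion.** The point holds as a correctable distortion of a few descriptive safety rows, not a loss of data. For a completer whose recorded last dose is the day before Month 6, 1 of 6 scheduled post-baseline samples is left out of the last-value and worst-value rows, and the last on-treatment value moves back to Month 5. Over assumed rates of 2% to 10%, the worst liver category is lowered for 1.8% to 5.9% of affected completers per parameter with independent visits and 0.9% to 3.7% with correlation 0.5. It falls to none if abnormalities fully persist. The overall effect scales with the share of completers whose termination date is entered as the day before Month 6, which the documents do not give; nor do they say how often withdrawal samples come late. The albumin error does not depend on any date. It should be fixed, because as written the rule can classify identical subjects differently.

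**What to change.** In SAP 4.8.4, define on-treatment laboratory values as those collected after the first dose and up to the last main-study dose plus a short stated tail, for example 7 days. Then:

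- always include the Month 6 visit sample of a subject who completes the treatment period;
- include a withdrawal-visit sample only if it falls within the tail;
- exclude any sample taken after the first extension-study dose;
- take the lowest on-treatment value as worst for albumin.

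The ±14-day mapping for by-visit tables is unchanged. The protocol passages on whether a dose is taken at the Month 6 visit (10.2.2.1, 10.2.2.5, 10.5 and 11.2) must be reconciled, because the recorded last-dose date depends on them.

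The cost is a short rewording of the rule, one clause for albumin and one flag in the laboratory dataset. The downside is that a few values up to a week off drug would count as on-treatment. Naming the Month 6 visit alone would be a smaller change, but it would not recover the withdrawal samples.
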